### AEs

The definitions, reporting, and follow-up of AEs, SAEs, and potential pregnancies are described in Section 9.

### Phosphorylated HSP27 (PD endpoint)

Phosphorylated HSP27 (pHSP27) and total HSP27 in sorbitol stimulated peripheral whole

blood and in skeletal muscle will be measured at the timepoints specified in the Schedule of Assessments ([Table 2](#)). The Visit 4 (pre-treatment) value will be defined as the baseline value for change from baseline calculations. pHSP27 and total HSP27 values will be transformed using the natural log function. The change from baseline in pHSP27/total HSP27 in sorbitol stimulated whole blood and change from baseline in pHSP27/total HSP27 in muscle natural log values will be calculated at each post-treatment timepoint. Post-treatment will be obtained at the estimated  $C_{max}$  time (eg, 4h  $\pm$  1h).

#### **Plasma and Muscle PK parameters of Losmapimod (PK endpoint)**

There will be no PK parameters calculated. Plasma and muscle concentrations of losmapimod will be summarised by timepoint. PK samples will be collected at the timepoints specified in the Schedule of Assessments ([Table 2](#)) Details about sample collection, handling, and processing will be described in the study reference manual.

#### **MRI**

Whole-body Dixon MRI for lean muscle tissue and muscle replacement by fat (fat fraction) will be measured at the timepoints specified in the Schedule of Assessments ([Table 2](#)) to evaluate the change from the pre-treatment period in skeletal muscle lean tissue volume, and tissue replacement by fat. The change from baseline in fat fraction will be calculated at each post-treatment timepoint.

Standardised MRI protocols for imaging in neuromuscular disorders, including the measurement of skeletal muscle tissue replacement by fat using the Dixon technique ([Dixon, 1984](#)), have been recommended as a result of 2 consortia organised by the Treat NeuroMuscular Disease network ([Hollingsworth et al., 2012](#)). The MRI technique to be used in this study is a standardised, objective, quantitative technique with automatic skeletal muscle segmentation and fat fraction analyses via robust algorithms using Dixon imaging to measure the extent of skeletal muscle tissue replacement by fat in subjects with FSHD1.

Details including the specific muscles and muscle regions to be analysed will be described in the study MRI manual. The study MRI manual will also describe in detail all the steps involved in the acquisition, transmission, quality evaluation, and analysis of MRI images between the study site and the central reader.

#### **Ultrasound**

Ultrasound for skeletal muscle echogenicity will be measured at the timepoints specified in the Schedule of Assessments ([Table 2](#)) to evaluate the change from the pre-treatment period in skeletal muscle echogenicity. Details about the muscles to be assessed and the quantification of changes in echogenicity will be described in the study reference manual.

### **Skeletal Muscle Needle Biopsy and Blood Products**

Needle biopsies of skeletal muscle tissue will be collected at Visit 4 (pre-treatment) and at Visit 5 (on-treatment) as specified in the Schedule of Assessments (Table 2).

DUX4 activity and other disease related gene transcripts in skeletal muscle will be measured at the timepoints specified in the Schedule of Assessments (Table 2) by RNA sequencing and by qPCR in a panel of DUX4-regulated gene transcripts. Details on the derivation of the DUX4 activity exploratory efficacy endpoint will be provided in the Statistical Analysis Plan (SAP). Discovery for biomarkers of DUX4 activity and biomarkers of FSHD muscle injury or repair will be done in plasma and serum samples drawn at timepoints specified in the Schedule of Assessments using protein assays on a panel of proteins hypothesised to be dysregulated in disease. Whole-venous blood will be purified to plasma and serum to support these measurements.

Physicians experienced in skeletal muscle needle biopsy will perform the muscle biopsies. These needle muscle biopsies in general, take only a short time and are well-tolerated, including when done repeatedly. In 1 large series, no complications were reported in 400 consecutive skeletal muscle needle biopsies (Edwards et al., 1983). Rarely (<1%), there can be superficial infection or haematomas (Edwards et al., 1983). Several muscles from the legs are safely accessible by needle for biopsy.

The choice of the muscle(s) to be biopsied in this study will be informed by skeletal muscle MRI during the screening visit. Muscles in the thigh and the calf on either side will be evaluated for eligibility by MRI using a central reader. This information will be communicated to the study site. Based on the information provided by the central reader and their own experience with muscle biopsy, the site will select the muscle or muscles for biopsy. The muscle(s) approved for biopsy will be those demonstrating a STIR-positive signal with some but not excessive fatty infiltration on the screening MRI, as determined by the central reader. The same muscle will be biopsied twice when possible.

The muscle tissue collected at each biopsy will be analysed by central laboratories for DUX4 activity using RNA sequencing and a molecular panel of DUX4-regulated gene transcripts using qPCR, drug concentration, and target engagement.

The specific details of the biopsy procedures, materials to be provided, materials to be resourced locally, personnel qualification, vendors, and methods for tissue collection, processing and analysis will be specified in the study reference manual. The study reference manual will be version controlled and may be updated as needed if the ongoing quality review of the tissue samples warrants changes. The informed consent will describe the muscle biopsy procedure for the subjects, as well as the risks and mitigations related to the procedure.

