### 3.3 ANALYSES FOR SECONDARY ENDPOINTS

#### Phosphorylated HSP27 (PD endpoint)

Phosphorylated HSP27 (pHSP27) and total HSP27 (tHSP27) in peripheral whole blood with ex-vivo sorbitol stimulation and in skeletal muscle (without sorbitol stimulation) will be measured at the time points specified in the schedule of assessments (Tables 2 and 3 of the protocol).

The Visit 4 (pre-treatment) value will be defined as the baseline value for change from baseline calculations.

All pHSP27 and tHSP27 values will be transformed using the natural logarithm function and will be summarized at each visit. If there is any value reported as zero (0) in either of the two parameters, a factor of 0.01 will be added to all observations prior to the log transformation.

The change from baseline in pHSP27, tHSP27 and pHSP27/tHSP27 - in sorbitol stimulated whole blood and in muscle - will be summarized at each post-treatment timepoint. The geometric mean for fold change from baseline and percent change from baseline (and 95% confidence interval) in pHSP27/total HSP27 will be calculated for each post-treatment timepoint. The percent change from baseline will be calculated as:

Percent change from baseline =  $100 * (\exp(\text{mean of change from baseline on the log-transformed scale}) - 1)$ .

Post-treatment will be also obtained at the estimated  $C_{\max}$  time (e.g. 4h+-1h).

Summaries presented for subjects with second muscle biopsy at 4 weeks post-treatment (Biopsy Cohort Week 4), 8 weeks post-treatment (Biopsy Cohort Week 8), and for all subjects combined.

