#### 3.4.1 Assessment of DUX4 Activity

A subset of DUX4-gene transcripts will be measured in skeletal muscle biopsies, using validated QRT-PCR assays, to measure the treatment effect of losmapimod on aberrant DUX4 activity. A composite DUX4 score will be derived for each patient, at each time point based on normalized gene expression values for the panel of pre-selected genes.

The quantification of gene expression using qPCR, normalization of qPCR and derivation of the composite DUX4 score are conducted at a central laboratory (Q2 Lab Solutions). For details on assay validation, gene subset selection criteria/process, and derivation of the composite DUX4 Score, see Appendices 1 – 5.

All subjects will undergo up to two muscle biopsies; one at baseline, pre-treatment (Visit 4, Week 8 ± 1 week), the second on-treatment muscle biopsy approximately 4 or 8 weeks later (Visit 5, Week 14 ± 2 weeks). Up to 8 subjects will have the second on-treatment biopsy at 4 weeks (Biopsy Cohort Week 4) and up to 8 subjects will have the second on-treatment biopsy at 8 weeks (Biopsy Cohort Week 8).

The DUX4 composite score will be summarized as change from pre-treatment (Week 8 biopsy) to on treatment (Week 14 ± 2 weeks). If the pre-treatment or on-treatment DUX-4 results are unavailable, then the assessment is considered missing. Missing results will be imputed by mean, worst case, and median methods ([Section 2.3.6](#)).

The individual components of the composite DUX4 score will also be summarized at each timepoint, along with change from baseline for post-treatment visits.

An additional DUX4 composite score based on a simple average, across all 6 genes, per subject, per timepoint, will be summarized as change from pre-treatment (Week 8 biopsy) to on treatment (Week 14 ± 2 weeks), to assess if a simpler approach to creating a composite score leads to equivalent interpretations of study results.

Similarly, another additional DUX4 composite score based on a simple average, across the top 2 genes, per subject, per timepoint, will be summarized as change from pre-treatment (Week 8 biopsy) to on treatment (Week 14 ± 2 weeks).

Composite scores based on simple averages will not be imputed. Summaries presented for Biopsy Cohort Week 4, Biopsy Cohort Week 8, and overall.

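### Change in muscle pHSP27 and DUX4 is summarised over same-muscle and switched-muscle biopsy pairs together, with nothing planned to tell the two apart

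*Protocol*

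**What the plan says.** **Choice of muscle (Protocol 8.2, skeletal muscle needle biopsy).** "Muscles in the thigh and the calf on either side will be evaluated for eligibility by MRI using a central reader". The central reader approves muscles on a common MRI profile: a STIR-positive signal with limited fat. From that information and its own experience, "the site will select the muscle or muscles for biopsy". For the second biopsy the rule is: "The same muscle will be biopsied twice when possible".

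**DUX4 (SAP 3.4.1).** "The DUX4 composite score will be summarized as change from pre-treatment (Week 8 biopsy) to on treatment". The strata are biopsy timing only: "Summaries presented for Biopsy Cohort Week 4, Biopsy Cohort Week 8, and overall". Missingness depends on whether a result exists: "If the pre-treatment or on-treatment DUX-4 results are unavailable, then the assessment is considered missing". Missing composite scores are then imputed (SAP 2.3.6).

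**Muscle pHSP27 (SAP 3.3).** "The change from baseline in pHSP27, tHSP27 and pHSP27/tHSP27 - in sorbitol stimulated whole blood and in muscle - will be summarized" at each post-treatment timepoint, again by biopsy-week cohort and combined.

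**Other places a safeguard could sit.** SAP 2.2 defines one analysis set, the safety set. SAP 3.6 limits sensitivity analyses to an alternative baseline, and its endpoint list contains no biopsy measure. The subgroup variables in SAP 2.5 are blacked out, and those analyses are optional.

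**The concern.** A within-subject change is read as the effect of time on treatment because everything else about the subject is held fixed. If the second sample comes from another muscle, or the same muscle on the other side, that no longer holds: the difference between the two sites is added to any on-treatment change. Protocol 1.1 describes asymmetric muscle involvement as common in FSHD, so two sites in one person need not start at the same level. The design has a single arm, so there is no comparison group in which similar switching could cancel.

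What is at stake is the interpretation of estimates. Muscle target engagement is a secondary endpoint, and the biopsy is the planned direct measure of DUX4 activity in muscle. Protocol 1.3.4 says the results will guide further development. With at most 14 pairs, a few switched ones can move a mean, and the planned tables would not let a reader see it.

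**Working it through.** **1. Is there a rule that separates the pairs?** The biopsy text permits a switch. Set beside it, SAP 2.2 (analysis set), 2.3.6 (missing data), 3.3 and 3.4.1 (strata) and 3.6 (sensitivity) contain no condition on muscle or side. A switched pair therefore enters the same mean as a same-muscle pair, both overall and within each biopsy-week cohort. By contrast, SAP Appendix 6 computes longitudinal MRI change muscle by muscle and drops a muscle that cannot be analysed at either timepoint. The top-2 DUX4 score adds a further dependence: its two transcripts are chosen per subject at baseline, so in a switched pair they are picked in one muscle and re-measured in another.

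**2. Inputs.** There is no planned figure to reproduce, because Protocol 4.4 says the sample size has no statistical basis. The number of subjects is 14 (Protocol 4.4); taking 14 complete pairs is an assumption. The number of switched pairs, k, and the between-muscle difference, b, are not in the documents. I take k = 1 to 4 and b = 1 or 2 log2 units in either direction.

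**3. Shift in the mean.** On a log2 scale the mean change moves by (k/14) × mean b. Back-transformed, the apparent change with no drug effect is 2^(shift) - 1. For k = 3 and b = 1: 3/14 × 1 = 0.214; 2^(-0.214) - 1 = -13.8%; 2^(+0.214) - 1 = +16.0%.

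| k of 14 | b = 1, second muscle lower / higher | b = 2, second muscle lower / higher |
|---|---|---|
| 1 | -4.8% / +5.1% | -9.4% / +10.4% |
| 2 | -9.4% / +10.4% | -18.0% / +21.9% |
| 3 | -13.8% / +16.0% | -25.7% / +34.6% |
| 4 | -18.0% / +21.9% | -32.7% / +48.6% |

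In a cohort of 7 (an even split is assumed), 2 switched pairs at b = 1 give a shift of 2/7 = 0.286 log2 units, that is -18.0% or +21.9%. If the true change on this scale were a 50% reduction, k = 3 and b = 1 would show 0.5 × 0.862 = 0.431 (a 56.9% fall) or 0.5 × 1.160 = 0.580 (a 42.0% fall).

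**4. If between-muscle differences average zero.** There is then no bias, only noise. The standard error is multiplied by √(1 + (k/14) × r), where r is the extra variance in a switched pair divided by the variance of same-muscle change. For k = 3 and r = 0.5, 1 and 2 this gives 1.05, 1.10 and 1.20. At r = 2, k = 1 gives 1.07 and k = 4 gives 1.25.

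**5. Price of using same-muscle pairs only.** The 95% CI half-width, t(0.975, n-1)/√n in SD units, is 0.577 at n = 14, 0.635 at n = 12, 0.672 at n = 11 and 0.715 at n = 10. The step from 14 to 11 pairs widens the interval by 0.672/0.577 - 1 = 16%.

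**The case against.** The strongest reply is that nothing in the documents shows that a switch took place, and that the design already makes any substitute resemble the first choice. Approved muscles meet one MRI standard set by a central reader. qPCR values are normalised to reference genes, and pHSP27 is also analysed as a ratio to total HSP27. This stands as mitigation: these steps narrow between-muscle differences. They do not equalise them, and they do not identify which pairs are affected.

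A second reply is that the percentages do not apply to the main DUX4 score. This is correct. SAP Appendix 4 defines that score as a per-subject median of MAD-standardised delta Ct values, with no return to a percent scale. For muscle pHSP27 the SAP does back-transform a log mean, but the documents give no figure for how far that ratio differs between muscles.

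A third reply is that Protocol 10.1.1 promises listings of all collected data, SAP 3.5 allows further exploratory analyses, and the blacked-out subgroup list or the study reference manual might cover muscle identity. Listings may well show the site if it is recorded, but they do not separate the change summaries. The other routes are optional or cannot be checked.

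A reader might infer that the biopsy results are biased towards benefit, or might set the 14% beside the decrease of 50% or more that Protocol 13.1 anticipates. The documents do not support either step. The direction is unknown, a systematic gap between first-choice and substitute muscles is conjecture, and the composite is on another scale. Nor are the biopsies the trial's only view of mechanism: blood pHSP27 and circulating proteins do not depend on the biopsy site.

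**Conclusion.** The gap is real and minor. The protocol permits a change of muscle or side, and in the text available no SAP rule, set, stratum or sensitivity summary distinguishes such pairs. Whether it matters depends on facts the documents do not contain: the number of switches, which may be zero, and the size and sign of between-muscle differences. Depending on these, the effect could be nil, a wider interval, an apparent fall or a masked effect.

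The illustration of about -14% or +16% assumes 14 complete pairs, 3 switches and a uniform 1 log2 difference on the expression scale. It shows sensitivity; it is not an estimate of bias. Severity is low because DUX4 is exploratory, muscle pHSP27 is secondary, and SAP 2.4 plans no formal tests. Protocol 10.3.1 does describe a paired comparison with zero for pHSP27, and SAP 3.3 a 95% interval for the pHSP27/total HSP27 ratio. That is one more reason for readers to know which pairs lie behind the muscle estimates.

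**What to change.** In SAP 3.3 and 3.4.1, derive a flag for each biopsy pair: same muscle and side, or not. Keep the all-pairs summary as planned and add beside it, as a sensitivity summary, the change in same-muscle pairs, at least for the overall group. Show the flag, with the muscle and side at each biopsy, in the listings.

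The cost is one derived variable from the biopsy-site record and one extra row per table. No procedure changes and no data are dropped. The downside is precision: the same-muscle summary rests on fewer pairs, and splitting it again by biopsy cohort would leave very small cells, so the overall row is the useful one. If the flag shows no switches, a single sentence in the report closes the question.

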## **RWS**

RWS with and without weights will be measured at Baseline and at the timepoints specified in the Schedule of Assessments. (Table 2). The functional workspace is a component of the RWS

The RWS uses a 3-dimensional (3D) vision-based sensor system (using a single system depth-ranging sensor) that can unobtrusively detect an individual's range of motion that reflects individual shoulder and proximal arm upper extremity function.

During the evaluation, subjects are seated in front of the Microsoft Kinect sensor and a large TV screen for demonstration and undergo a standardised upper extremity movement protocol under the supervision of a study clinical evaluator. The Microsoft Kinect sensor-tracks the 3D hand trajectory and transforms the movements into a body-centric coordinate system. Each individual's RWS envelope is reconstructed in a graphical output. Each side's RWS envelope is divided into 4 quadrants (2 upper quadrants and 2 lower quadrants, 2 ipsilateral and 2 contralateral quadrants) with the shoulder joint serving as the origin. The absolute total RWS surface envelope area (in  $m^2$ ) as well as areas for each of the quadrants will be calculated by a central reader after quality assessment of the raw data. Scaling of the data by each person's arm length will allow normalisation for comparison between subjects. (Han et al., 2015). The change from baseline in RWS measures will be calculated at each on-treatment visit. Further details about the RWS are provided in the study reference manual.

## **TUG**

TUG will be measured at the timepoints specified in the Schedule of Assessments (Table 2).

The classic TUG test is a simple test used to assess a person's mobility and requires both static and dynamic balance and muscle strength. It measures the time that a person takes to rise from a chair, walk 3 meters, turn around, walk back to the chair, and sit down.

The FSHD-optimised TUG test is the usual classic TUG but adds the component for getting up from a laying position on a low-lying mat at the start of the test and laying back down on the back at the end of the test. The change from baseline in both classic TUG and FSHD-optimised TUG measures will be calculated at each post-dose timepoint.

## **Muscle Strength**

Muscle strength will be measured by quantitative dynamometry with hand-held devices (manual) and with bed frame equipment, and with Manual Muscle Testing (MMT) at the timepoints specified in the Schedule of Assessments (Table 2). Dynamometry is used to objectively assess the strength of multiple muscles or muscle groups. Manual Muscle

Testing is one of the most commonly used forms of muscle testing. With MMT, the subject is instructed to hold the corresponding limb or appropriate body part to be tested at the end of its available range while the evaluator provides opposing manual resistance. Manual Muscle Testing will be assessed in the extension period of the study. The procedure for dynamometry assessments and MMT for specific muscles to be measured will be described in a separate study reference manual. The change from baseline in muscle strength measures will be calculated at each post-dose assessment.

### **MFM Domain 1**

The MFM domain 1 will be measured by a physical therapist at the timepoints specified in the Schedule of Assessments (Table 2).

The MFM scale assesses the severity of the motor deficit in the main neuromuscular diseases as determined by a physical therapist and has good psychometric properties. The score is reproducible, the coefficients of the interrater reliability are good or excellent. The total score provides a good measure of the overall functional severity across various domains. This trial will only use Domain 1. Domain 1 focuses on ambulation and transfers ability. The change from baseline in MFM domain 1 scores will be calculated at each post-dose timepoint. Details will be described in the study reference manual.

### **FSHD PROs**

#### ***FSHD-HI***

The FSHD-HI will be measured at the timepoints specified in the Schedule of Assessments (Table 2).

The FSHD-HI is a 15-domain questionnaire designed and based on subject interviews to measure total FSHD health-related quality-of-life, including both motor impairment and the social and emotional impact of FSHD. A total of 116 questions are combined into a total score and domain scores, the scores are transformed onto a percentage scale, with 100 representing maximal disability, and lower scores representing decreasing disability. The scoring is done centrally by the vendor who developed the tool.

The change from baseline in FSHD-HI total score will be calculated at each post-dose timepoint.

#### ***FSHD-RODS***

The FSHD-RODS will be measured at the timepoints specified in the Schedule of Assessments (Table 2).

The FSHD-RODS is a patient-reported, linearly weighted scale that precisely measures ADLs and participation in subjects with FSHD using 50 items based on the Rasch model. Details will be described in the study reference manual.

The change from baseline in FSHD-RODS score will be calculated at each post-dose timepoint.

#### Real-world Mobility Assessments

Each subject's activity will be monitored in the outpatient setting intermittently from Visit 2 to the end of the study. Wearable activity monitoring devices will be provided to each subject. The training for the devices will be done at the clinical site before they are handed the wearable devices. The subjects will be able to place their devices on their body by themselves. One device is placed on 1 arm, and 1 device goes on 1 leg.

The exact time of wearing the devices will be variable for each subject, but the duration of wearing the device will be similar. It is expected that the subject will wear the devices as soon as they wake up in the morning and are able to put on the device. Subjects may be asked to perform some standardised physical activity after putting on and before removing the devices.

Subjects who do not put on the device during the study period may be contacted to remind them to put on the device or to offer assistance.

Detailed instructions and details on wearables will be provided to the study site and subjects in a separate study reference manual.

Subjects will be asked to record the use of ankle-foot-orthotics or other assistive devices on a paper calendar during the time they are wearing the wearables, if applicable.

Real world mobility will be assessed only in the main part of the study. Real world mobility will not be assessed in the extension part of the study.

